In this proposed study, peer-support groups with buddy members will be arranged in each daycare center. Three pairs of buddies and hence about 6 participants will be formed per group. A total of 6 buddy pairs and 2 groups will be formed per daycare center. Buddy peers will encourage each other to do functional exercises regularly or to perform functional exercises together. The time and place for the practice will be decided among buddy members. A member in each group will be nominated as the leader to assist in the liaison and coordination of group activities. The group will perform weekly group-based functional exercises, and the time and place for the practice will be decided among group members. The group will be encouraged to hold monthly gatherings with their fitness instructor in order to strengthen social support.

Study design

A two-arm cluster randomized controlled trial will be employed in this proposed study (see details in Fig 1). According to the Social Welfare Department of Hong Kong, there are 98 daycare centers for the elderly in 2023 (14). Daycare centers for the elderly located in 3 regions in Hong Kong will be invited to participate in the intervention. The PLBI will be conducted for twelve weeks.

Sample size and participants

The required sample size is calculated based on the hypothesized effect sizes, and the likely rates of participant drop-out for the outcomes. The estimated sample size is 198 with an effect size of 0.25, α of 0.05 and power of 0.95 (15). With the anticipation of a 20% participant drop-out rate, this led to a required number of 120 participants per group. Therefore, 10 daycare centers for the elderly in Hong Kong will be invited to participate in this study.

Physical literacy-based intervention group (PLBI)

Inclusion criteria will be: 1) those aged 65 to 74 years old who are registered in a daycare center/unit for the elderly in Hong Kong, 2) the ability to walk eight meters without assistance (16), and 3) able to read and write. Exclusion criteria will include 1) neurological disease which impairs mobility, cardiovascular disease which results in shortness of breath or angina on walking up one flight of stairs, and 2) cognitive impairment. Participants' cognitive function will be screened by the Chinese Mini-Mental State Examination (17, 18), and those who score below 24 will be excluded.

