SPSS version 28 for Windows will be used for data analysis. Internal consistency reliability coefficients (Cronbach alpha) will be calculated for all sub-scales within the psychometric questionnaires. A cut-off score of 0.7 will be used to determine acceptable reliability. Descriptive statistics (means and standard deviations) will be calculated for participants' primary and secondary outcomes (objective and self-reported) at three-time points. Multilevel modeling methods were used to account for the clustered nature of the data. Specifically, we used three-level (time within older adults within daycare center) regression analyses to examine the effects of group (experimental vs control), time (baseline, post-test and follow-up), and the group-time interaction (i.e., "intervention effect") on the primary and secondary outcomes. Covariates such as age, gender, BMI, education, and socioeconomic status will be included in the analysis. Bonferroni post hoc analyses will be conducted to determine contributing factors to the significance of F values, and the confidence level will be set at 95% to maintain statistical reliability for all the analyses.

Evaluation plan

At post-intervention, in-depth interviews of a group of 8 - 12 participants will be conducted to explore their experiences in participating in the intervention, the level of satisfaction with the intervention, and the barriers and expediter in performing the PLBI as instructed. DBRW will also be material for evaluation analysis. The reasons why participants dropped out of the study will also be recorded. Additionally, participants will be invited to fill in a process evaluation survey which assesses their level of involvement and level of satisfaction with the intervention.

Reference

1. Morgan K. Applying the TARGET Pedagogical Principles in Physical Education to Enhance Students' Physical Literacy. *Journal of Physical Education, Recreation & Dance*. 2019;90(1):9-14.

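### Enrolling 120 per group does not cover the stated 20% drop-out: about 192 completers are expected, 6 fewer than the 198 the plan starts from

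*Combined protocol and SAP*

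**What the plan says.** The sample-size argument is a few sentences in the section on sample size and participants. It begins: "The estimated sample size is 198 with an effect size of 0.25, α of 0.05 and power of 0.95", with a citation to a general power-analysis program. It continues: "With the anticipation of a 20% participant drop-out rate, this led to a required number of 120 participants per group". The study design section gives the number of arms: "A two-arm cluster randomized controlled trial will be employed in this proposed study".

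The plan does not say whether 198 is a total or a per-group figure, which statistical test produced it, which effect-size metric the 0.25 refers to, or how the drop-out allowance was applied. No other section gives a different drop-out rate or a different target.

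The data analysis section describes the model: "Specifically, we used three-level (time within older adults within daycare center) regression analyses to examine the effects of group". It does not describe how missing data will be handled.

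**The concern.** A drop-out allowance exists so that the number left after the expected losses is still the number the power calculation needs. The plan presents 120 per group as the result of applying 20% drop-out to 198. If 20% of those enrolled leave, 120 per group does not leave 198. The sentence therefore claims a margin that the enrolment target does not provide, and the stated power of 0.95 is attached to a sample the plan does not expect to have at the end.

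This is the document's only sample-size justification. If the same step were reused when the calculation is redone for the clustered design, the error would carry into a larger number.

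**Working it through.** **Inputs, all from the section on sample size and participants unless noted**

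- Sample before drop-out: 198 (read as a total, see below)
- Drop-out: 20%
- Enrolment: 120 per group
- Groups: 2 (study design section)
- Effect size 0.25, α 0.05, power 0.95

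**Is 198 a total?** The plan does not say. Read per group, 198 already exceeds 120 before any losses, so the two figures could not be reconciled. Read as a total it is 99 per group, which is compatible with 120 after inflation. This is also the reading most favourable to the plan, so it is used here.

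**Reproducing the plan's 120**

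- Multiplying by (1 + d): 198 × 1.20 = 237.6. Half of that is 118.8, so 119 per group, and 120 if rounded up further.
- Dividing by (1 − d): 198 / 0.80 = 247.5, so 248 in total or 124 per group.

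The printed 120 is consistent with the multiplication and not with the division. That the multiplication was used is an inference, because no formula is stated. The shortfall below does not depend on it.

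**Expected completers**

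- Enrolled: 2 × 120 = 240
- Expected to complete: 240 × (1 − 0.20) = 192, or 96 per group
- Shortfall: 198 − 192 = 6, or 3 per group; 6 / 198 = 3.0%
- Largest drop-out that still leaves 198: 1 − 198/240 = 17.5%
- Check on the division: 248 × 0.80 = 198.4, which meets 198

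**Illustrative effect on power.** The test and effect-size metric are not stated. The figures below assume Cohen's f = 0.25 and a two-sided comparison of two groups at α = 0.05, with power from the noncentral F distribution on 1 and N − 2 degrees of freedom. Clustering is ignored throughout.

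- Independent groups, one measurement: λ = N × 0.25².
- Repeated-measures between-group test, 3 measurements, correlation ρ: λ = N × 0.25² × 3 / (1 + 2ρ).

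| Assumed test | Power at 198 | Power at 192 |
|---|---|---|
| Independent groups (λ = 12.375 and 12.0) | 0.938 | 0.931 |
| Repeated measures, ρ = 0.9 (λ = 13.26 and 12.86) | 0.952 | 0.946 |
| Repeated measures, ρ = 0.5 (λ = 18.56 and 18.0) | 0.990 | 0.988 |

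The loss is under one percentage point in every row. None of these is shown to be the plan's own calculation. For power 0.95, the independent-groups test needs 210. The repeated-measures test needs 196 at ρ = 0.9 and 142 at ρ = 0.5. So 198 does not follow from the stated inputs alone. The ρ = 0.9 row comes close to it, but no correlation appears in the plan.

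**The case against.** The strongest objection is that this hardly matters. Three people per group, against a round and uncertain drop-out rate, changes no decision in the trial, and the power figures rest on a test, a metric and a correlation that the plan does not give. That stands, and it is why the point is minor. The arithmetic on 198, 20% and 120 needs none of those assumptions.

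A second objection is that completers are not the analysis sample. A three-level model with time nested in person can use baseline and week-12 measurements from someone lost before week 18, so the effective loss may be smaller than six people. This is also fair, although the plan does not describe its handling of missing data. It does not rescue the sentence: by inflating for drop-out, the plan itself treats 198 as the number wanted after losses.

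Third, the plan calls 198 an estimated sample size and uses neither the word total nor the word completers. Reading it as the total to be retained is therefore an inference, but the per-group reading makes the gap much larger.

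Finally, the same section has bigger gaps. It states no intracluster correlation or design effect. The centre numbers are also unclear: 6 buddy pairs, about 12 people, in each of 10 centres is about 120, not 240, unless 10 centres per group is meant. A full recalculation would replace all these figures. Those are separate points and do not make the drop-out step correct.

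**Conclusion.** The concern holds, as a minor point. At the plan's own 20% drop-out, 240 enrolled gives 192 expected completers against 198, a shortfall of 6 (3%). The target tolerates 17.5% drop-out, not 20%. This rests on reading 198 as a total and on equal groups, which 120 per group implies. The practical effect is small, and partial data from people who leave may reduce it further. What is wrong is the claim that 120 per group follows from 198 and 20% drop-out.

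**What to change.** Keep 120 per group and say what it supports, for example: *We will enrol 120 people per group, 240 overall. If 20% drop out, about 192 will complete; 198 will be retained only if drop-out is no more than 17.5%.* Name the test, effect-size metric and any assumed correlation that produced 198, and report the power of that test at 192.

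The cost is a sentence and a slightly less favourable power figure, with no change to enrolment. The total of 240 should be confirmed when the centre and buddy-pair numbers are reconciled.

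The alternative is to meet the allowance in full with 124 per group, 8 more people in total. There is little reason to make that change alone, because a recalculation that allows for clustering would replace the figure. When that is done, apply drop-out by dividing by (1 − 0.20), not by multiplying by 1.20.

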The research team will randomly send a series of email messages and invitation letters to daycare centers in accordance with their district via a computer-generated

randomization sequence (GraphPad Software, Inc.) by a statistician who is blinded to the allocation of participating daycare centers. After the daycare centers agree to participate, a leaflet package, which describes the theoretical background, timeframe, and main objectives/learning goals, will be delivered to the staff of daycare centers. Then an introductory meeting with staff will be held to illustrate practical details related to the intervention. The proposed program will be publicized in the participating elderly daycare centers through posters and pamphlets, where the efficacy and benefits of PLBI will be briefly outlined. Recruitment will follow by setting up counters supported by the staff in the participating centers. Those who express interest will have their eligibility screened through a short questionnaire based on the inclusion and exclusion criteria. More detailed information about the study will be given to the eligible participants. Written informed consent will be obtained.

Control group

Participants will follow the inclusion and exclusion criteria of the PLBI group. Participants will not receive PLBI intervention treatment. However, participants in the control group will be given the same treatment (program and activities) after all data has been collected.

Outcome measures

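### Recruitment posters and pamphlets outline the efficacy of PLBI before consent, although the trial is meant to test it; use the same neutral publicity in all centres of both arms

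*Combined protocol and SAP*

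**What the plan says.** Recruitment is described under Physical literacy-based intervention group (PLBI). After a centre agrees, its staff receive a leaflet package on background, timeframe and aims. "Then an introductory meeting with staff will be held to illustrate practical details related to the intervention". As the next step, the programme is "publicized in the participating elderly daycare centers through posters and pamphlets, where the efficacy and benefits of PLBI will be briefly outlined". Counters, which centre staff help to run, are opened afterwards to take volunteers. Interested people are screened with a short questionnaire. "More detailed information about the study will be given to the eligible participants", and written consent is the last step.

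Under Control group, the plan says "Participants will follow the inclusion and exclusion criteria of the PLBI group". Controls receive no PLBI during the trial, but "participants in the control group will be given the same treatment (program and activities) after all data has been collected".

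The opening section on PLBI says that the efficacy of interventions outside the school setting is still to be shown, and that older adults have been neglected in earlier PLBI work. Outcome measures sets assessments at weeks 0, 12 and 18. It assigns the objective measures to blinded assessors and the self-report measures to research assistants, for whom no blinding is stated.

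**The concern.** The publicity text credits PLBI itself with efficacy, which is what the trial is designed to find out. People read this before they have full information and before they consent. They later learn that they either have the programme or must wait for it. Those who were told that it works and then receive it may report, and try, more. Those who were told that it works and then wait may do the reverse. A difference between arms that arises this way would be read as an intervention effect, because the plan defines that effect as the group-by-time interaction, and expectation would also act after baseline.

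**Working it through.** The plan states no figure on this point, so the check sets the relevant sections side by side.

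1. **Order of events** (recruitment text). Centre agrees; staff leaflet; staff meeting; posters and pamphlets; counters; screening; detailed information; consent. The publicity comes before both full information and consent.

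2. **Claim against evidence.** The publicity attributes efficacy to PLBI. The opening section regards efficacy outside schools as unproven. Parts 1 and 3 cite supportive studies, but of exercise and of writing, not of the four-part package. The posters are not in the documents and may only summarise those studies. This is a tension in the text, not a proven contradiction.

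3. **Who can be influenced.** Participants know whether they attend a training programme, so they cannot be blinded. The blinding clause in Outcome measures attaches to the assessors of the objective measures.

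4. **Which outcomes are exposed.** Leaving demographics aside, the self-report section lists five instruments:
   - self-rated: IPAQ short form, PPLI, PWB, friend support = 4;
   - a performance test: MoCA-B = 1;
   - total 4 + 1 = 5, so 4 of 5 are self-rated.

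   The primary outcomes are the SPPB and accelerometry. Blinded assessors limit observer bias there. They do not control how hard a participant tries, or how active a participant is over seven days of wear.

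5. **What the analysis can remove.** Data analysis names five covariates (age, gender, BMI, education, socioeconomic status). None of the five measures motivation or expectation, but the list is open. The section Motivation and confidence says that PWB captures motivation, and it is collected at baseline, so an imbalance in motivation between arms can be checked. Expectation itself is not measured. The group-by-time term removes stable differences in level, but not differences in expected change.

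6. **Disclosure of allocation.** The visible text does not say when or by whom a centre's arm is revealed. Two cues bear on it: the statistician who sends the invitations is blinded to centre allocation, and intervention participants receive their notebook only at the end of the baseline stage (Part 3). Both are compatible with disclosure after baseline; neither settles it. Study design refers to Fig 1 for details.

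7. **Size.** The documents give nothing from which an expectation effect, or the share of it due to publicity, could be estimated. None is computed.

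**The case against.** The strongest case against runs as follows. Nobody outside the study has seen the posters. The plan says only that they will be brief, and they may fairly report evidence on the components. Nothing visible shows that publicity differs by arm, and if all centres see the same posters, the message is common to both. Divergence then starts when people learn their arm, which neutral posters would not prevent. Some expectation comes with any consent discussion and any delayed control. The main exposure is on secondary outcomes.

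Most of this stands, and it limits the point to a modest one. It does not remove it: a shared message that the programme works raises the stakes of learning one's arm, so a common cause can still feed a divergent response. The plan's wording also names PLBI, not its components, as the thing with efficacy.

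Three stronger readings are tempting, and the documents do not support them.
- *The trial is unblinded.* The assessors of the objective primary outcomes are blinded.
- *Recruiters or participants know the arm when people volunteer, or only PLBI centres are publicised.* The recruitment text does sit under the PLBI heading, but it speaks of participating centres without distinction, and eligibility is the same in both arms. Fig 1 is not shown, so silence in the visible text is not a gap in the plan.
- *Motivation goes unmeasured.* The plan itself assigns PWB to that role and collects it at baseline.

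**Conclusion.** The point holds as an inexpensive improvement to a stated procedure. Publicity that outlines efficacy precedes consent in a trial that is meant to test that efficacy, with participants who cannot be blinded and a control group that waits. The plausible consequence is additional arm-divergent expectation, mainly on the four self-rated secondary instruments and possibly on effort or activity in the two primary measures. Its size is unknown, and removing the claim would reduce expectation, not abolish it.

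The conclusion assumes that the posters will say what the plan says they will, and that participants learn their arm before the post-intervention assessment, which follows from the nature of the programme. It does not depend on Fig 1. The timing of allocation disclosure is a separate matter on which no defect is shown; it is a question for the sponsor.

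**What to change.** Replace the publicity wording with a statement that identical posters and pamphlets will be used in all centres of both arms, describing the study, what taking part involves and the fact that the programme's benefit is not yet known, with no efficacy claim.

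As a query, ask the sponsor to confirm that staff, recruiters and participants learn each centre's arm only after consent and baseline assessment in that centre. If Fig 1 already shows this, one sentence in the text is enough.

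Baseline PWB can be tabulated by arm as a check on motivation; this needs no new data, and it does not stand in for a measure of expectation.

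The cost is rewording the posters and pamphlets and one or two sentences in the protocol. Sample size, visits, outcomes and the analysis model do not change. The one foreseeable downside is that recruitment may be slightly slower.

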Assessment or charting progress in relation to physical literacy is essential, as this will help clarify policymakers' understanding of the concept as well as individuals' appreciation of their physical literacy journeys, and how they might develop physical literacy through a lifespan (2). Physical literacy is an individualized personal journey so any assessment trying to support this journey should be relative to the individual and their progress and must reflect the changes over time (19). Therefore, this study will adopt both objective and self-reported measures to cover the elements and domains of physical literacy. Participants will be evaluated at baseline (week 0), post-intervention (week 12), and at a 6-week follow-up (week 18). All of them will be conducted at daycare centers for the elderly. The self-reported measurements will be administered by research assistants while the objective measurements will be performed by certified physical fitness assessors and health professionals who are blinded to the randomization for avoiding bias.

Objective measure (primary outcomes)

Physical competence

The Short Physical Performance Battery (SPPB) will be used to measure the physical competence within the physical literacy of older adults (16). Huang et al. (18) suggested using a combined and comprehensive kit of assessment tools to measure physical competence, and the SPPB was reported to be able to measure complex capabilities with excellent test-retest reliability, especially in community-dwelling older adults. It is a group of measures that combines the results of the gait speed, chair stand and balance tests, which consist of balance, a timed eight-foot walk and chair stands. The scores range from zero (worst performance) to 12 (best performance). It has been used as a predictive tool for possible disability and can aid in monitoring function in older people. The reliability of SPPB has been reported as $ICC = 0.75 - 0.89$ for all measures.

Daily behavior

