Accelerometers (Actigraph wGT3X-BT) will be used to measure the physical activity engagement levels of participants, and are categorized as sedentary, light, moderate and vigorous. Data was collected in 60 s epochs to account for elderly people's natural activity levels, as it was shown to present the most acceptable classification accuracy for accelerometer use among older adults (20). The cut-points developed by Aguilar-Farías et al. was applied to identifying intensity levels (20). Participants will wear accelerometers at the waist to measure their physical activity engagement levels for at least 8 hours per day, for seven consecutive days.

Self-report measures (secondary outcomes)

Demographic information

Demographic information including age, gender, BMI (height and weight), education, and socio-economic status will be included in the starting part of the questionnaire set, in order to acquire personal characteristics for further analysis.

Daily behavior

International Physical Activity Questionnaire – short form is the short version of the International Physical Activity Questionnaire used to measure self-reported physical activity levels. They will be required to report on the total duration of different types of physical activity which lasted at least 10 uninterrupted minutes in the last 7 days.

Example item included: During the last 7 days, how many days did you do vigorous physical activities?

Knowledge and understanding

Montreal Cognitive Assessment (MoCA) is a 30-question brief and sensitive test used for detecting Alzheimer's disease and measuring executive functions and multiple cognitive domains. It is widely adopted for older adults and will be used to assess knowledge and understanding of physical literacy among the elderly. MoCA-B is a revised MoCA test. The Chinese Version of MoCA-B tests nine cognitive domains (executive function, language, orientation, calculation, conceptual thinking, memory, visual perception, attention, and concentration), and has been reported as a reliable cognitive screening test across all education levels in Chinese elderly adults (21), with high acceptance and good reliability.

Physical literacy

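### The primary accelerometer outcome has an 8-hour daily wear floor, no all-waking-hours instruction and no stated handling of wear time, so a change in wear that differs by arm could not be told from a change in activity

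*Combined protocol and SAP*

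**What the plan says.** The combined protocol and SAP places accelerometry under Objective measure (primary outcomes), Daily behavior, beside the SPPB. Activity levels "are categorized as sedentary, light, moderate and vigorous", using 60-second epochs and published cut-points. The wear rule is one clause: participants wear the device at the waist "for at least 8 hours per day, for seven consecutive days". Assessments are at weeks 0, 12 and 18 (Outcome measures).

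The Data analysis section fits a three-level model and takes the group-by-time interaction as the intervention effect. On adjustment it says "Covariates such as age, gender, BMI, education, and socioeconomic status will be included in the analysis".

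Two parts of the intervention matter here. For buddy practice, "The time and place for the practice will be decided among buddy members", and the weekly group exercise is left to group members in the same way (Part 4). From the end of the baseline stage, intervention participants also keep a daily notebook that includes physical activity, and they share it with the instructor and peers (Part 3). Controls do not receive the programme until all data have been collected.

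Nowhere does the document ask for wear during all waking hours, say which hours to cover, give a non-wear rule, define the accelerometer summary variable (minutes per day, share of wear time or counts), or state an adjustment for wear time.

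**The concern.** Time in an intensity category can accrue only while the device is on. Under the stated rule, a participant who wears it for 8 hours and then takes it off has complied fully, and so has one who wears it from rising to bedtime. Two problems follow.

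- **Which hours are worn.** Part of the activity that the programme tries to build happens when participants choose. A compliant participant can leave it unrecorded, which would pull the estimate towards no effect.
- **How many hours are worn.** If minutes per category are analysed, longer wear looks like more time in each category. After baseline, only the intervention arm logs and discusses its activity each day, so a shift in wear confined to that arm is plausible. It would be read as intervention effect, or would mask one.

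Blinding the assessors does not help, because participants decide when the device is on.

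**Working it through.** The plan gives no figure to reproduce. The check has three steps. All waking-day and activity values below are assumptions, because the document gives none.

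**1. What the floor covers.** Share of the waking day = 8 / waking hours. For 14, 15, 16 and 18 waking hours this is 57%, 53%, 50% and 44%. At the floor, roughly half the waking day is observed.

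**2. How recorded minutes depend on wear.** Assume 15 waking hours and 40 active minutes spread evenly. Recorded minutes = 40 × h / 15.

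| Wear (h) | Recorded active minutes | Minutes per hour worn |
|---|---|---|
| 8 | 21.3 | 2.67 |
| 12 | 32.0 | 2.67 |
| 14 | 37.3 | 2.67 |

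Behaviour is identical in every row. Each extra hour adds 40 / 15 = 2.7 minutes. The rate per hour worn is constant, so a share-of-wear-time summary removes this part of the problem.

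A second assumed profile is 65% of wear time sedentary, 30% light and 5% moderate to vigorous. It gives 312, 144 and 24 minutes at 8 hours (480 minutes worn), and 546, 252 and 42 at 14 hours (840 minutes worn). One hour of wear moves the three by 39, 18 and 3 minutes.

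Dropping the even spread brings out the other problem. If all 40 minutes fall outside 8 worn hours, the recorded share is 0 / 480 = 0%. If all fall inside, it is 40 / 480 = 8.3%. Over the full 15 hours it is 40 / 900 = 4.4%. A share of wear time therefore corrects for the amount of wear but not for the choice of hours.

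**3. What reaches the intervention effect.** Let W be mean wear in an arm at a visit and r the minutes recorded per hour worn. With no change in behaviour, the spurious interaction at week 12 is

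r × [(W at week 12 − W at week 0) in PLBI − (W at week 12 − W at week 0) in control].

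- If the arms differ by a constant amount, each bracketed change is unaffected and the difference is zero.
- If both arms change by the same amount between visits, the difference is zero.
- If wear rises by one hour more in PLBI than in control, the spurious effect is 2.7 active minutes per day under the first profile, or 39 sedentary and 18 light minutes under the second.

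The same holds at week 18. Only the third case biases the stated effect.

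**The case against.** The strongest reply is that the clause sets a minimum. It fits a valid-day criterion as well as an instruction, and many participants may wear the device much longer. That stands: the text does not settle the reading, and half a waking day is the position at the floor, not the expected wear. But an open-ended floor is also what lets wear differ between people, arms and visits.

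It can also be said that a correction is not excluded. No summary variable is defined, so a share of wear time remains possible, and the covariate list is introduced as examples. That stands too: the accurate statement is that no correction is stated. For a primary outcome, the choice should be made before the data are seen.

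Three stronger readings are tempting, and the document does not support them.

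- *Any wear difference between arms or visits biases the result.* The effect is a group-by-time interaction with a baseline measure, so only a change that differs by arm does so.
- *The trial cannot say whether daily behaviour changed.* The short-form IPAQ also covers the last 7 days, including hours when the device is off. It is self-reported and secondary, so it does not repair the primary outcome, but it is evidence on the same question.
- *Differential wear or missed practice will occur.* Both are plausible from the design. Neither is shown.

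The illustrations also have limits. The contrast between 8 and 14 hours is not an expected difference between arms, and the plan gives no SD or target difference in minutes against which to judge 2.7 minutes.

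**Conclusion.** The point holds as a gap in the measurement and analysis of a primary outcome. The stated wear rule allows activity at self-chosen times to go unrecorded. If minutes per intensity are analysed, a post-baseline change in wear that differs by arm could not be separated from a change in behaviour. The direction is not predictable, since unrecorded practice dilutes the effect while longer wear in one arm can inflate it.

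The size is illustrative: about 2.7 active minutes per hour of differential change, given 15 waking hours and 40 evenly spread active minutes. Movements in sedentary and light time are larger under the second assumed profile. The amount-of-wear argument would largely fall away if the outcome proved to be a share of wear time. The choice-of-hours argument would remain. This should be changed because the remedy is cheap, not because bias has been demonstrated.

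**What to change.** 1. **Wear instruction.** Ask participants in both arms to wear the device during all waking hours for the seven days, and keep 8 hours as the minimum for a valid day. This addresses which hours are captured.
2. **Analysis.** Name the summary variable in the Data analysis section. Analyse each intensity as a share of wear time, or include wear time at each visit as a covariate. Baseline wear alone would not address a post-baseline change. State how wear is identified from the epochs.
3. **Reporting.** Give wear hours by arm and visit, so that a differential change can be seen.

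Parts of the text are in the past tense ("Data was collected in 60 s epochs to account for elderly people's natural activity levels"), so collection may have started. If it has, leave the wear instruction as it is, because changing it partway would itself alter wear between visits. Apply items 2 and 3, which need only the recorded epoch data; the question of which hours were worn then stays as a stated limitation.

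The cost is a revised instruction and a short addition to the analysis text, with the same device and the same seven days. The downside is some added burden from longer daily wear.
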